8.4.4 Other Analyses/Assessments

For continuous variables, descriptive statistics will include the number of non-missing values, mean, standard deviation, median, min and maximum. For categorical variables, descriptive statistics will include counts and percentages per category.

Descriptive statistics with mean, standard deviation and 95% CI will be calculated for baseline JAK/STAT3 Signaling activation and Wilcoxon rank tests will be used to determine the significant difference on baseline JAK/STAT3 Signaling activation between responders and non-responders.

Descriptive statistics with mean, standard deviation and 95% CI will be calculated for baseline and change in STAT1/STAT3 activation and Wilcoxon rank tests will be used to determine the significant difference on baseline and change in STAT1/STAT3 activation between responders and non-responders.

Descriptive statistics with mean, standard deviation and 95% CI will be calculated for baseline SHP-2 overexpression and Wilcoxon rank tests will be used to determine the significant difference on baseline SHP-2 overexpression between responders and non-responders.

8.5 **Evaluation of Safety**

Analyses will be performed for all patients having received at least 14 days' worth of study drug. The study will use the NCI CTCAE v4.0.

9 **Study Management**

9.1 **Pre-study Documentation**

This study will be conducted in accordance with the ethical principles that have their origin in the Declaration of Helsinki as stated in 21 CFR §312.120(c)(4); consistent with GCP and all applicable regulatory requirements.

Before initiating this trial, the Investigator will have written and dated approval from the Institutional Review Board for the protocol, written informed consent form, participant recruitment materials, and any other written information to be provided to participants before any protocol related procedures are performed on any participants.

The clinical investigation will not begin until either FDA has determined that the study under the Investigational Drug Application (IND) is allowed to proceed or the Investigator has received a letter from FDA stating that the study is exempt from IND requirements.

Phase 2 - Ruxolitinib Page 52 of 67

The Investigator must comply with the applicable regulations in Title 21 of the Code of Federal Regulations (21 CFR §50, §54, and §312), GCP/ICH guidelines, and all applicable regulatory requirements. The IRB must comply with the regulations in 21 CFR §56 and applicable regulatory requirements.

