Each patient receiving ruxolitinib will be evaluable for safety. The safety parameters include all laboratory tests and hematological abnormalities, physical findings, and spontaneous reports of adverse events reported to the investigator by patients.

Each patient will be assessed periodically for the development of any toxicity as outlined in Section 6 Study Procedures and Observations. Toxicity will be assessed according to the NCI

Phase 2 - Ruxolitinib Page 32 of 67

CTCAE v4.0. Dose adjustments will be made according to the system showing the greatest degree of toxicity.

We will monitor for the following anticipated adverse events:

Anemia

In the two Phase 3 clinical studies, median time to onset of first CTCAE Grade 2 or higher anemia was approximately 6 weeks. One patient (0.3%) discontinued treatment because of anemia. In patients receiving ruxolitinib, mean decreases in hemoglobin reached a nadir of approximately 1.5 to 2.0 g/dL below baseline after 8 to 12 weeks of therapy and then gradually recovered to reach a new steady state that was approximately 1.0 g/dL below baseline. This pattern was observed in patients regardless of whether they had received transfusions during therapy.

In the randomized, placebo-controlled study, 60% of patients treated with Jakafi and 38% of patients receiving placebo received red blood cell transfusions during randomized treatment. Among transfused patients, the median number of units transfused per month was 1.2 in patients treated with ruxolitinib and 1.7 in placebo treated patients.

Thrombocytopenia

In the two Phase 3 clinical studies, in patients who developed Grade 3 or 4 thrombocytopenia, the median time to onset was approximately 8 weeks. Thrombocytopenia was generally reversible with dose reduction or dose interruption. The median time to recovery of platelet counts above 50 X 10⁹/L was 14 days. Platelet transfusions were administered to 4.7% of patients receiving ruxolitinib and to 4.0% of patients receiving control regimens. Discontinuation of treatment because of thrombocytopenia occurred in 0.7% of patients receiving ruxolitinib and 0.9% of patients receiving control regimens. Patients with a platelet count of 100 X 10⁹/L to 200 X 10⁹/L before starting ruxolitinib had a higher frequency of Grade 3 or 4 thrombocytopenia compared to patients with a platelet count greater than 200 X 10⁹/L (16.5% versus 7.2%).

Neutropenia

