7.1 Evaluation of Efficacy: Antitumor Effect – Solid Tumors

Response and progression in this study will be evaluated using the new international criteria proposed by the Response Evaluation Criteria in Solid Tumors (RECIST) Committee [JNCI 92(3):205-216, 2000]. Changes in only the largest diameter (unidimensional measurement) of the tumor lesions are used in the RECIST v1.1 criteria (or International Workshop on Chronic Lymphocytic Leukemia [IWCLL]).

7.1.1 **Definitions**

Evaluable for toxicity

All patients will be evaluable for toxicity from the time of their first treatment with the study drug.

Evaluable for objective response

Only those patients who have measurable disease present at baseline, have received at least one cycle of therapy, and have had their disease re-evaluated will be considered evaluable for response. These patients will have their response classified according to the definitions stated below. (Note: Patients who exhibit objective disease progression prior to the end of Cycle 1 will also be considered evaluable.)

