7.2 Evaluation of Safety

Analyses will be performed for all patients having received at least one dose of study drug. The study will use the CTCAE v4.0 for reporting of non-hematologic adverse events and modified criteria for hematologic adverse events, see Appendix 2.

The Principal Investigator at the UCSF Coordinating Center will hold the role of Study Chair. The Study Chair is responsible for the overall conduct of the study and for monitoring its safety and progress at all participating sites.

7.3 **Definitions of Adverse Events**

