8.2.2 Replacement Policy

Because this is an open label study with limited number of patients, 23 accrued eligible patients with clinical tumor assessments and biomarkers measurements at baseline and the end of study window are required for the study. Additional patients will be enrolled to replace patients without clinical tumor assessments and completed biomarker measurements for both time points at least one of the five biomarkers of interest. However, all patients will be followed and included for safety assessments.

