8.3 Interim Analyses and Stopping Rules

This is an open label biomarkers study. No interim analysis is planned.

8.4 **Analyses Plans**

8.4.1 **Analysis Populations**

Safety Population

The safety population will include all enrolled patients who receive at least one dose of ruxolitinib and have the potential to complete pharmacodynamics biomarkers assessments at baseline and the end of study treatment window. Although the risk from specimen collections for biomarker assessment is limited and low, all patients will be evaluable for toxicity and safety assessment of ruxolitinib. Patients who are determined ineligible after enrollment or who are not evaluable for safety analysis (e.g. due to withdrawal of consent or failure of specimens collection as not related to tumor progression and not treatment-related toxicity) will be replaced (see section 8.2.2 for details).

Efficacy Population

The efficacy population for the primary endpoint of 35% or greater reduction in tumor size will include all enrolled patients who have measurable disease present at baseline and have completed tumor assessment at the end of study window. Patients who are determined ineligible after enrollment or who are not evaluable for safety analysis (e.g. due to withdrawal of consent or failure of specimens collection as not related to tumor progression and not treatment-related toxicity) will be replaced (see section 8.2.2 for details).

Phase 2 - Ruxolitinib Page 50 of 67

Version date: 03-22-2023 Protocol CC# 16201

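### Section 8.5 limits the safety analyses to patients with 14 days' worth of drug, while 5.6, 7.1.1, 7.2 and 8.2.2 include all treated patients; if 8.5 were followed, early toxicity stops would be missing from the safety report

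*Combined protocol and SAP*

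**What the plan says.** Two sections of the protocol are headed Evaluation of Safety, and they define different analysis sets.

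- Section 8.5: "Analyses will be performed for all patients having received at least 14 days' worth of study drug".
- Section 7.2: "Analyses will be performed for all patients having received at least one dose of study drug".

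Three other sections agree with 7.2.

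- Section 5.6: "Each patient receiving ruxolitinib will be evaluable for safety".
- Section 7.1.1: "All patients will be evaluable for toxicity from the time of their first treatment with the study drug".
- Section 8.2.2, on patients who are replaced: "However, all patients will be followed and included for safety assessments".

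Section 8.4.1 defines a Safety Population. It starts from one dose, but adds that patients must "have the potential to complete pharmacodynamics biomarkers assessments at baseline and the end of study treatment window". Its next sentence says that "all patients will be evaluable for toxicity and safety assessment of ruxolitinib". The one after provides for replacing patients who are "not evaluable for safety analysis (e.g. due to withdrawal of consent or failure of specimens collection", and the Efficacy Population paragraph repeats that replacement sentence.

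Fourteen days also appears as the minimum treatment for a patient to count as evaluable, in 3.5.1 and 6.3.2.1. In 3.5.1 that status is tied to screening tissue and a response assessment.

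**The concern.** Whether a patient reaches 14 days' worth of drug depends partly on how well the drug is tolerated. Section 5.5 stops drug and removes the patient for related grade 3-4 non-hematologic toxicity (with an exception for manageable electrolyte abnormalities) and for grade 3 or higher thrombocytopenia or neutropenia. It also allows removal for intolerable non-hematologic toxicity of any grade. A set limited to patients with 14 days' worth of drug therefore leaves out those whose toxicity ended treatment early.

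Tolerability is a secondary objective (2.2). Section 2.3.2 says it will be reported through tabulated toxicities, surgical complications and length of hospital stay. A patient outside the analysis set is missing from all three. With two thresholds in the plan and no order of precedence, the safety denominator could also be chosen after the data are seen.

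**Working it through.** **1. Is the contradiction real?** Set side by side, the rules are:

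| Section | Who enters the safety analysis |
|---|---|
| 5.6 | every patient receiving drug |
| 7.1.1 | all patients, from first treatment |
| 7.2 | one dose or more |
| 8.2.2 | all patients, including those replaced |
| 8.4.1 | one dose or more, with a biomarker-potential clause; then all patients |
| 8.5 | 14 days' worth or more |

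Nothing labels 8.5 a sensitivity or supplementary set, and no section is given precedence. The 8.5 rule cannot hold together with 5.6, 7.1.1, 7.2 or 8.2.2.

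**2. Who is lost under 8.5?** Planned treatment is 14-21 days (3.4, 6.3.2). A patient removed under 5.5 before 14 days' worth of drug cannot reach the threshold. A toxicity stop after that point stays in. Patients who did not stop for toxicity can also be lost. Section 3.4 ends treatment for progression, withdrawal of consent or noncompliance, and 5.5 allows a hold of up to one week: a full hold followed by surgery on day 14 leaves about 14 − 7 = 7 days of drug.

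**3. Which way does the reported rate move?** The plan states no figure to reproduce here. Let

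- p = true toxicity-stop rate among treated patients,
- s = share of toxicity stops excluded by 8.5,
- q = share of all other treated patients excluded by 8.5.

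Reported rate = p(1 − s) / [1 − ps − q(1 − p)].

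This is below p when 1 − s < 1 − ps − q(1 − p), that is, when s(1 − p) > q(1 − p), or simply s > q. It equals p when s = q and exceeds p when s < q.

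**4. Illustration.** The documents give none of p, s and q for this population. I take p = 10% because it is the mean of the Beta(1, 9) prior in 5.2, 1/(1 + 9). It is not a forecast. The values of s and q are assumptions.

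| s | q | Calculation | Reported rate |
|---|---|---|---|
| 10% | 0 | 0.09 / 0.99 | 9.1% |
| 50% | 0 | 0.05 / 0.95 | 5.3% |
| 100% | 0 | 0 / 0.90 | 0% |
| 50% | 20% | 0.05 / (1 − 0.05 − 0.18) = 0.05 / 0.77 | 6.5% |
| 10% | 20% | 0.09 / (1 − 0.01 − 0.18) = 0.09 / 0.81 | 11.1% |

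In counts, if all 45 planned patients were treated (an assumption), p = 10% is 4.5 expected stops. With s = 50% and q = 0, 2.25 of them are left out, and 2.25 / 42.75 = 5.3%.

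**5. What does not depend on 8.5?** The de-escalation rule (5.2, 8.2.3) counts toxicity discontinuations with no 14-day minimum. Adverse event entry and review (7.4, 7.6) and expedited reporting (7.7) have no such minimum either. The primary analysis (8.4.2) concerns biomarkers and tumor size.

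**The case against.** The best defence is that 8.5 stands alone. Four sections include all treated patients, and 8.4.1, the section that defines analysis populations, also starts from one dose and refers to 8.2.2 for details. Its biomarker clause asks for the potential to complete assessments, not for completion. The specimen-failure example in its replacement sentence is limited to failures unrelated to progression or treatment toxicity. On toxicity stops, then, 8.4.1 leans towards inclusion, and the sponsor may well intend the one-dose set. This stands as a limit on the claim: patients would be lost if 8.5 were followed, and it is not certain that they will be. It does not remove the contradiction, because 8.5 is in the statistical chapter and is explicit.

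A second objection is that few patients may be affected. Section 5.5 calls clinically significant toxicity unexpected in the treatment window. Also, 2.3.2 does not name a toxicity-stop rate among the safety summaries, so the figures above concern an inferred summary. Both points are fair, and they are why the figures are illustration only.

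A reader might also infer that surgery on day 14 itself fails the threshold. With a first dose on the morning of day 1 and the last on the morning of surgery, the count is 2 × 14 − 1 = 27 doses, or 13.5 days' worth. The documents do not support resting anything on this. Section 6.3.2.1 makes fourteen days the minimum and 6.3.2.3 allows surgery on day 14, so the plan evidently treats such a patient as meeting it.

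**Conclusion.** The contradiction is certain. Section 8.5 conflicts with 5.6, 7.1.1, 7.2 and 8.2.2, and 8.4.1 leans the other way without settling the matter. If 8.5 were followed, early toxicity stops would be left out of the descriptive report for a secondary objective.

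A reader might go further and conclude that the reported stop rate must be biased downward. The documents do not support that. The rate falls only if the excluded share of toxicity stops exceeds the excluded share of other patients, and neither share is given. In the assumed cases a true 10% reads anywhere from 0% to 11.1%. The omission of early toxicity stops is built into the 8.5 rule; the size, and even the sign, of the effect on the rate is not known.

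Nor do the documents support reading this as a failure of safety oversight. The events would still be recorded, reviewed and counted in the monitoring rule. The defect is confined to who enters the safety analysis, and it is worth correcting before that analysis is run.

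**What to change.** - **Section 8.5:** replace the sentence so that the safety analyses cover every patient who took at least one dose of ruxolitinib.
- **Section 8.4.1, Safety Population:** end the first sentence after the one-dose condition, deleting the clause on the potential to complete biomarker assessments.
- **Section 8.4.1, Safety and Efficacy Population paragraphs:** in the replacement sentence of each, refer to patients who are not evaluable for biomarker analysis instead of safety analysis. The sentence appears twice and both copies need the change.
- **Section 8.4.1:** state, in line with 8.2.2, that replaced patients who took at least one dose stay in the safety population.
- **14-day threshold:** keep it only for biomarker and response evaluability, as in 3.5.1 and 6.3.2.1.

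The cost is a handful of wording changes in two sections. No new data, visits or patients are needed.

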- If participants experience any grade 3-4 ruxolitinib-related non-hematologic toxicities in the neo-adjuvant window, the study drug will be discontinued and they will be removed from the study. (Exception: Patients with asymptomatic grade 3 electrolyte abnormalities manageable with repletion) Patients may also be removed from study for intolerable non-hematologic toxicities of any grade, which persist despite optimal medical management.
- If participants experience grade ≥ 3 thrombocytopenia or neutropenia, ruxolitinib will be discontinued and they will be removed from the study.
- Grade 3 anemia does not require discontinuation from protocol. Patients may be transfused per discretion of the treating physicians.
- For mild or moderate (grade 1 or 2) side effects that are difficult to tolerate, treatment
 may be held for up to 1 week. Treatment may be resumed at the same dose, if there is
 improvement by at least one grade. Dose delays more than 1 week will not be permitted.
 If treatment is restarted, study physicians should aim for at least 3 days of ruxolitinib
 exposure prior to planned surgery.

In two Phase 3 clinical studies of ruxolitinib in myelofibrosis, the median time to onset of first CTCAE grade two or higher anemia was 6 weeks, and approximately 8 weeks until onset of grade 3 or 4 thrombocytopenia. In nearly all cases, ruxolitinib-induced anemia and thrombocytopenia could be reversed with dose reduction or interruption; occasionally red blood cell or platelet transfusions were required. Thus, given the short 2-3 weeks of treatment during this study, it is expected that few, if any, participants will develop hematologic abnormalities. Moreover, participants in the current study do not have a primary bone marrow malignancy which is the target of ruxolitinib and thus predisposes to hematologic toxicity. Any participants that experience anemia or thrombocytopenia may be transfused if deemed necessary by the treating physician.

Although clinically significant hematologic and non-hematologic toxicity is unexpected during the 14-21 days of protocol treatment in patients with operable HNSCC, a continuous monitoring rule for excess toxicity will be instituted. Please see Section 5.6 below.

5.6 **Monitoring and Toxicity Management**

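### Section 8.5 limits safety analyses to patients with at least 14 days' worth of drug, contradicting the all-treated rule elsewhere, and no section says which governs

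*Combined protocol and SAP*

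**What the plan says.** Tolerability of brief pre-operative ruxolitinib is a secondary objective (2.2), to be reported descriptively by CTCAE tabulation (2.3.2). The document describes who is analysed for it in six places:

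- 8.5: "Analyses will be performed for all patients having received at least 14 days" worth of study drug.
- 7.2: "Analyses will be performed for all patients having received at least one dose of study drug".
- 5.6: "Each patient receiving ruxolitinib will be evaluable for safety".
- 7.1.1: "All patients will be evaluable for toxicity from the time of their first treatment".
- 8.2.2, on patients who are replaced: "all patients will be followed and included for safety assessments".
- 8.4.1: a named safety population that needs one dose and also the prospect of finishing the biomarker assessments at both time points. The same paragraph then says "all patients will be evaluable for toxicity and safety assessment of ruxolitinib".

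Section 5.5 decides who stops early. Related grade 3-4 non-hematologic toxicity ends treatment, apart from asymptomatic grade 3 electrolyte abnormalities that can be managed with repletion. For grade 3 or higher thrombocytopenia or neutropenia, "ruxolitinib will be discontinued and they will be removed from the study". For hard-to-tolerate grade 1-2 effects, treatment "may be held for up to 1 week".

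On data entry, 7.4 and Appendix 2 section 3.1 put grade 3 and higher events into the trial database, while 7.6 puts in all adverse events.

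**The concern.** A tolerability analysis has to include the patients who did not tolerate the drug. Under 8.5, whether a patient is analysed depends on how long the patient stayed on drug, and 5.5 makes that depend on toxicity. Anyone stopped for a qualifying toxicity before reaching 14 days' worth would vanish from both numerator and denominator. The remaining group would be described as the study's safety experience although it was selected for having lasted about two weeks.

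The other sections would avoid this, but the plan does not rank them. The 14-day figure is also the plan's minimum for being evaluable (3.5.1, 6.3.2.1), so an analyst working from the statistical section could take 8.5 as intended. The named population in 8.4.1 does not settle the matter, because its biomarker condition can be read as excluding treated patients.

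**Working it through.** **1. The sections side by side**

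| Section | Who is in the safety analysis | A treated patient stopped for toxicity on, say, day 8 |
|---|---|---|
| 8.5 | at least 14 days' worth of drug | out |
| 7.2 | at least one dose | in |
| 5.6, 7.1.1 | every treated patient | in |
| 8.2.2 | all patients, including those replaced | in |
| 8.4.1, definition | one dose plus prospect of completing biomarkers | unclear |
| 8.4.1, next sentence | all patients | in |

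Section 8.4.1 goes on to mention patients who are not evaluable for safety, giving failed specimen collection as one example. That fits neither its own second sentence nor 8.2.2. No sentence in the document gives any of these rules precedence.

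**2. The plan's own safety figures**

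Table 5.2 uses a Beta(1, 9) prior, whose mean is 1/(1 + 9) = 10%. With r discontinuations among n participants, the posterior is Beta(1 + r, 9 + n - r), and the tabulated probability is its upper tail at 0.33. For 5 of 6, Beta(6, 10) gives .629, and the binomial tail at .33 is .017. For 14 of 33, the values are .590 and .167. All ten rows reproduce to three decimals, and each boundary is the smallest count whose posterior probability exceeds .50. The rule counts discontinuations among participants treated (5.2, 8.2.3), so 8.5 does not enter it.

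**3. Effect of following 8.5**

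Inputs:
- N = 45 treated. Section 3.2 gives 45 as accrual; that all are treated is assumed.
- p = 10% true toxicity discontinuation, the prior mean in 5.2.
- f = share of those stops before day 14. The documents do not give it. Stops spread evenly over a course of L days give f = 14/L. This is an assumption, with L = 28, 21 and 14 as the range.
- Everyone who does not stop for toxicity is assumed to receive 14 days' worth.

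Formulas: dropped = Npf; rate shown under 8.5 = p(1 - f) / (1 - pf).

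| L | f | Dropped | Left in the 8.5 set | Stops still visible | Rate shown |
|---|---|---|---|---|---|
| 28 | .50 | 45 × .10 × .50 = 2.25 | 42.75 | 2.25 | 5.3% |
| 21 | .667 | 45 × .10 × .667 = 3.0 | 42.0 | 1.5 | 3.6% |
| 14 | 1.00 | 45 × .10 × 1.00 = 4.5 | 40.5 | 0 | 0% |

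The rate shown does not depend on N. In whole patients, 5 stops that are all early are 5/45 = 11.1% of those treated and 0/40 under 8.5. If no stop came before day 14 (f = 0), there would be no bias.

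**4. Adverse event entry**

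Under 7.4 and Appendix 2 a grade 1-2 event need not be entered; under 7.6 it must be. A CTCAE table covering lower grades depends on which rule is followed.

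**The case against.** The strongest reply is that 8.5 is a stray sentence. It names no population; the named one is in 8.4.1 and starts from one dose. Section 7.2 uses nearly the same sentence with the one-dose threshold, and 5.6, 7.1.1 and 8.2.2 agree. The 14 days look carried over from the evaluability minimum. The numbers are also likely to be small. Section 5.5 calls clinically significant toxicity unexpected in this window. In the myelofibrosis trials, grade 3-4 thrombocytopenia took a median of about 8 weeks to appear, and in the placebo-controlled study adverse event discontinuation was 11.0% against 10.6% on placebo.

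Most of this stands. A reader might infer from 8.5 alone that early toxicity stoppers will be left out of the report. The documents do not support that as a settled rule, because four other sections, and one sentence of 8.4.1, point the other way. What remains is an unresolved contradiction. The reply does not remove it, since 8.5 is the evaluation-of-safety section of the statistical chapter and 8.4.1 carries a condition of its own.

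On data entry, a reader might infer that an intolerable grade 2 stop would be lost. Section 3.5.1 requires the reason for and date of withdrawal to be documented whatever the grade, so the stop itself is recorded. The gap concerns lower-grade events in the toxicity table.

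**Conclusion.** The point holds as an internal contradiction over the safety denominator, with a clear direction of bias if 8.5 is the rule applied. At the plan's 10% prior mean, with half to all of the stops before day 14, about 2 to 5 of 45 patients are dropped and a 10% rate shows as 0% to 5%. The timing of stops and 45 patients treated are assumptions. The direction needs only that some toxicity stops come before 14 days.

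Four stronger readings should be resisted:

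- Putting the 33% limit through the same formula gives 0% to 20%. Section 5.2 treats 33% as an upper bound, not an expected rate, so this is not a forecast.
- A one-week hold might seem always to leave a 14- to 20-day course with only 7 to 13 days' worth. Section 3.4 confines the 14-21 day window to cases without adverse event delays and allows up to 28 days when surgery is delayed, so drug may be extended.
- The de-escalation rule might seem compromised. It counts treated patients and is not.
- The absence of a separate on-drug event window and of change-from-baseline blood count tables might seem part of the error. Laboratory values are already safety parameters (5.6), attribution is assigned (7.4), and surgical complications are reported (2.3.2). Those tables are optional reporting detail.

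This is a correction to a secondary, descriptive objective.

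**What to change.** 1. In 8.5, analyse safety in all patients who receive at least one dose, matching 7.2.
2. In 8.4.1, delete the biomarker-completion condition from the safety population. The replacement sentence there should then concern biomarker evaluability only.
3. Report treatment-related discontinuations among all treated patients, with the day of stopping.
4. Secondary: bring 7.4 and Appendix 2 section 3.1 into line with 7.6, so that lower-grade toxicities are entered.

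Steps 1 and 2 change wording only. Step 3 uses withdrawal dates and reasons that 3.5.1 already requires. Step 4 adds some data entry for grade 1-2 events. No visits, tests or patients are added.
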